3.1 General Design

This is a prospective cohort study of 200 COVID-19 survivors and 80 control subjects without a known history of symptomatic COVID-19. Among survivors, we will prioritize subjects who had their index infection within the last 12 months. However, will allow for index infections acquired outside of this timeframe to facilitate enrollment. We will collect detailed measures of cardiovascular, pulmonary, renal structure and function, along with various other measures, as follows:

- (1) Endothelial function: flow-mediated brachial artery dilation and venous endothelial cell harvesting for molecular analyses.

CONFIDENTIAL

- (2) Arterial stiffness: carotid-femoral pulse wave velocity and carotid artery stiffness measurements.
- (3) Central pulse pressure and measurements of stroke volume and arterial compliance by impedance cardiography.
- (4) Subclinical atherosclerosis: carotid intima-media thickness and ankle-brachial index.
- (5) Pulmonary Function tests
- (6) Microvascular function: forearm ischemic vasodilation, and microvascular imaging with sublingual *in vivo* microscopy
- (7) A brief focused ultrasound test (liver, kidney, skeletal muscle, cardiac and carotid ultrasound), performed by a trained research team member.
- (8) Biosample collection (blood, urine and breath condensate)
- (9) A 6-minute walk test
- (10) A Kansas City Cardiomyopathy Questionnaire (KCCQ)
- (11) A subset of questions from the PROMIS Questionnaire to evaluate mental and physical function
- (12) A long COVID symptom Questionnaire
- (13) EQ-5D-5L Questionnaire
- (14) Social determinants of health questionnaire
- (15) Short Physical Performance Battery (SPPB)
- (16) In a subset of participants, we will also perform supine bicycle exercise tests to assess aerobic capacity (i.e., peak oxygen consumption, VO₂).

These tests are brief and in combination will take about ~5 hours. These assessments will be performed upon enrollment (baseline visit) and will be repeated at approximately 18-month intervals for a total of 3 tests (except for bicycle testing, which will only occur at baseline). Participants will also be followed prospectively for incident cardiovascular events via a combination of medical record reviews and phone calls *as needed in order to adjudicate specific outcomes. Adjudication of all-cause death may be assisted using data from the Social Security Death Index*. Expert clinical adjudicators will identify MACE (incident HF, MI, coronary revascularization, serious arrhythmia, stroke, peripheral artery disease [PAD], or death) by detailed review of hospitalization records.

Given availability of staff and/or Center for Human Phenomics Sciences staff to complete study procedures such as endothelial cell harvesting, supine bike VO₂ testing, and ultrasound, some participants may be asked to have their procedures done in different days to enhance data completeness and feasibility of scheduling.

3.2 Inclusion Criteria

- Subjects aged 18 years and older, male or female;
- Prior diagnosis of COVID-19 (acute symptoms consistent with COVID-19, confirmed by PCR, serologic or rapid antigen test) for the COVID-19 survivors group, or no confirmed or suspected prior history of symptomatic COVID-19 for the control group at the time of enrollment.

3.3 Exclusion Criteria

- Pregnant women;
- Inability to provide informed consent.
- History of CVD (defined as HF, MI, coronary revascularization, serious arrhythmia, stroke, greater than moderate valvular disease, any cardiomyopathy, or PAD), glomerular disease or polycystic kidney disease prior to enrollment.

CONFIDENTIAL

- End stage kidney disease (ESKD; defined as requiring persistent renal replacement therapy or prior kidney transplant) prior to enrollment
- History of chronic kidney disease (CKD) with eGFR <30 mL/min/1.73m² prior to enrollment. In participants without a history of CKD, a measurement of eGFR will not be required for enrollment.

3.4 Subject Recruitment

We will screen patients who received care at Penn Medicine for acute COVID-19 as well as patients referred to the post-COVID-19 clinic. We will also consider interested participants who reach out to us as a result of advertisements or other outreach efforts. Patients who meet the inclusion criteria will be identified and participants will be approached by a member of the study team for participation in the study. The study team will answer questions the subject has regarding participation, prior to signing the consent document.

3.5 Vulnerable Populations:

Children, pregnant women, fetuses, neonates, and prisoners are not included in this research study.

3.6 Study Procedures

3.6.1 Visit 1

A member of the study team will approach the patient for participation in the study and review the informed consent document with them. The study team will answer questions the subject has regarding participation, prior to signing the consent document.

After signing consent for participation in the study, the subject will undergo a series of brief procedures designed to obtain key phenotypes of various organ systems. All study procedures will be performed by a trained research team member. In combination, these procedures take ~2 hours.

Quality of Life Assessments: Subjects will then be given time to complete the short version of the Kansas City Cardiomyopathy Questionnaire (KCCQ), EQ-5D-5L, PROMIS Questionnaire and the long COVID symptom and impact tools.⁵⁷

Brief ultrasound protocol: we will use an Airexplorer Mach30 (SuperSonic Imagine; France; 510K K191007) ultrasound device. The ultrasound protocol will include the interrogations listed in **Table 1** and schematized in **Figure 1**. This ultrasound protocol is brief and will take ~ approximately 30 minutes in total. In patients in whom these areas are not accessible (amputation, bandages covering skin in areas of interrogation) or if time does not permit, the respective ultrasound acquisitions will not be performed. This procedure carries no known risks.

Table 1. Ultrasound scanning protocol

[figure not shown]
Acquisition	Description	Phenotypes of interest	Probe
Liver and kidney	Liver shear wave elastography in the supine to slightly left lateral decubitus position, with the probe on the lower right intercostal spaces, mid axillary line. B-mode, color Doppler and shear wave elastography acquisitions, followed by	Liver stiffness, echogenicity	Curved probe

CONFIDENTIAL

	unilateral kidney shear wave elastography from the anterolateral abdominal approach		
Pectoralis major, femoris rectus, and biceps thickness	
Pectoralis Major: Supine position. Right arm behind the neck. Probe on the right mid-axillary line, at the level of the angle of Lewis. Minimal compression.
 
Femoris Rectus: Supine position. Knee extended and relaxed. Midpoint between the right patella and anterosuperior iliac spine. Minimal compression.
 
Biceps: Supine position. Arms extended and relaxed. Midpoint between the acromion and elbow. Minimal compression.
 
B-mode, color Doppler and shear wave elastography acquisitions.
	Muscle thickness (sarcopenia), stiffness, echogenicity, and perfusion	High-frequency linear array probe
Carotid ultrasound	Right common carotid B-mode with color Doppler, single plane.	Carotid distensibility, wall stiffness, intima-media thickness, pulsatility, wave intensity	High-frequency linear array probe
Limited Cardiac and lung Ultrasound	
Limited parasternal, 4-chamber and 2-chamber view clips, mitral inflow and mitral/tricuspid annular tissue Doppler interrogations
 
Limited lung scan for lung B lines
	Diastolic function, myocardial strain and stiffness	Cardiac probe

CONFIDENTIAL

Figure 1. Sample images of liver elastography, carotid flow, rectus femoris, and pectoralis major thickness.

Pmj=pectoralis major; Pmi=pectoralis minor; R=rib

CONFIDENTIAL

Carotid images will be processed offline to assess the following metrics:

- 1) *Carotid intima media thickness (CIMT)*: We will measure CC-IMT in near and far walls and in the anterior, lateral and posterior projections using automated edge-detection software (Carotid Studio; Quipu, Italy). A carefully trained technician will measure CIMT at these sites as the distance between the intimal-luminal and the medial-adventitial interfaces of the carotid artery wall,⁵⁸ as done previously by our group.⁵⁹⁻⁶² CIMT will be computed as the mean of all measurements.
- 2) *Carotid stiffness*: We will perform time-resolved semi-automated wall tracking of the common carotid lumen diameter using view that best demonstrates both the near and far walls using automated edge-detection software (Carotid Studio; Quipu, Italy). As recently reviewed by our group, when performed assessments of local stiffness it is essential to avoid confounding by wave reflections.⁶³ Carotid distension waveforms will be used along with calibrated carotid tonometry waveforms to calculate local carotid PWV (a measure of wall stiffness), using an expression equivalent to the Bramwell-Hill equation, which combines pressure and diameter (ln(Dia)P method), which is not susceptible to wave reflections:
$$PWV = \sqrt{\frac{1}{2\rho} \frac{dP}{d\ln(Dia)}},$$
 where PWV is calculated from the slope of the linear segment of the loop constructed from plotting pressure as a function of the natural logarithm of diameter⁶⁴.

Impedance Cardiography (ICG): Study subjects will undergo a resting impedance cardiogram (Z-logic; Exxer, Buenos Aires, Argentina) for the evaluation of cardiac output, stroke volume, and cardiac contractility, which will allow the estimation of arterial compliance and other parameters of interest. ICG will be performed depending on time and equipment availability. ICG is a form of plethysmography that utilizes changes in thoracic electrical impedance to estimate changes in blood volume in the aorta and changes in fluid volume in the thorax. The ICG procedure involves the placement of electrical leads (similar to ECG leads) on the patient's neck and chest. A low-amplitude, high-frequency alternating current is delivered from some sensors while other sensors detect instantaneous changes in voltage. As suggested by Ohm's law, when a constant current is applied to the thorax, the changes in voltage are directly proportional to the changes in measured impedance. The overall thoracic electrical impedance, called base impedance (Z_0) is the sum of the impedances of the components of the thorax, including fat, cardiac and skeletal muscle, lung and vascular tissue, bone, and air. Changes from thoracic electrical impedance occur due to changes in lung volumes with respiration and changes in the volume and velocity of blood in the great vessels during systole and diastole. The rapidly changing component of chest impedance is filtered to remove the respiratory variation, leaving the impedance changes due to ventricular ejection. These impedance changes have been shown to be accurate predictors of stroke volume, and with the use of mathematical algorithms, ICG allows for accurate non-invasive measurements of stroke volume and cardiac output.^{65,66} This procedure is non-invasive and does not produce pain or discomfort to the subject.

Pulmonary Function Testing: We will perform a basic expired spirometry and measurements of CO diffusion capacity (DLCO) and lung volumes.⁶⁷ We will utilize an FDA-approved Easyone Pro Lab Respiratory Analysis System (NDD systems Andover, Massachusetts; 510K K161534). In this test, subjects perform a forced expiration into a disposable probe meter (spirometry), primarily to determine forced vital capacity and forced expiratory capacity in 1 s (FEV1). As recommended, DLCO measurements will be performed in duplicate for enhanced accuracy. In these measurements, participants will inspire CO gas one deep inspiration, followed by an ~8-10 second breath-hold, as tolerated, followed by normal breathing into the disposable mouthpiece for ~2 minutes, during which the machine measures the washout time of CO from the alveoli. Lung volumes will be performed by measuring the washout time of inhalation of 100% oxygen.

CONFIDENTIAL

This test will in total ~20 minutes. Pulmonary function tests will not be performed if participants are receiving >2L/min of supplemental oxygen.

Aerobic capacity: In a subset of participants who agree to additional testing, have no contraindications to exercise testing (such elevated fall risk or severely elevated blood pressure >180/100) and contingent on availability of equipment, personnel and funding, we will use a supine bicycle exercise protocol in conjunction with expired gas analysis to assess oxygen consumption (VO_2) during exercise. This subset of subjects will perform a maximal exertion limited exercise test using a graded-exercise protocol. We will use a supine cycle ergometer designed for stress echocardiography (Stress Echo Ergometer 1505, Medical Positioning, Inc, Kansas City, MO). Subjects will undergo expired gas analysis with a Parvo Medics True One 2400 device (Parvo Medics, Sandy, UT) or equivalent. Resistance began at 15 W for 3 minutes, increasing to 25 W for 3 minutes, and then increasing by 25 W every 3 minutes thereafter. Breath-by-breath information will be recorded. We will use custom-designed software already developed in Matlab (MathWorks, Natick, MA) at our lab for offline processing and quantification of all exercise data.⁶⁸ All data quantification will be blinded to treatment. Given costs considerations and funding availability, we will offer this additional component to former participants of the FERMIN trial (NCT04517396) but can be expanded to other participants as additional funding becomes available.

Arterial tonometry: Carotid-femoral PWV will be measured with arterial applanation tonometry, which considered the clinical gold-standard method for the assessment of large artery stiffness.^{63,69,70} We will use a commercially available system (SphygmoCor CVMS, AtCor Medical) with a high-fidelity applanation tonometer (Millar Instruments). This involves sequential recordings of carotid and femoral arterial waveforms using a pen-like high-fidelity applanation tonometer placed on top of the artery on the body surface, along with electrocardiographic measurements so that the R wave of the QRS can be used as a time-reference point to compare both recordings and compute the pulse transit time between the carotid and femoral locations. Surface measurements of distance between carotid and femoral sites are performed to estimate intra-aortic path length (80% of the direct body surface distance between the sites). Carotid-femoral PWV is computed as distance/transit time. Radial and carotid applanation tonometry will be performed as well. Brachial arterial pressures will be measured with a fully validated oscillometric device (Omron HEM 907-XL BP monitor; Omron Healthcare; 510K K032305 or BP+ device, 510K K121266). Arm circumference will be measured, and the appropriate cuff size will be placed. Radial waveforms will be calibrated with brachial systolic and diastolic pressures. Radial pressures will be used to calibrate the carotid pressure waveform, which serves as a surrogate of the central pressure waveform, and will be used to obtain central pulse pressure.

Flow mediated dilation (FMD): Brachial artery FMD and hyperemic flow velocity, which evaluate conduit artery endothelial function and microvascular function, respectively,^{71,72} are important indicators of vascular health and predictors of CV risk.^{73,74} FMD will be measured using a semi-automated device equipped with an *ad hoc* vascular ultrasound probe (UNEX Corporation, Nagoya, Japan). In this test, a brachial cuff is inflated to 50 mmHg above the systolic blood pressure, which is measured in advance. The inflation is held for 5 minutes, and the cuff is then deflated. The maximum diameter of the blood vessel of the same region is tracked continuously after deflation. The FMD is calculated as follows: $FMD (\%) = (\text{maximum diameter} - \text{diameter at rest}) \times 100/\text{diameter at rest}$. Hyperemic brachial artery flow velocity will be determined by using pulsed wave Doppler to detect the peak flow velocity during the first 15 seconds post-cuff release.⁷⁴⁻⁷⁶ During the test, we will use wireless near-infrared spectroscopy (NIRS) devices to measure microvascular oxygenation as feasible. We will use a wireless PortaMon device and a wireless PortaLite device (Artinis medical systems; The Netherlands) to measure forearm

CONFIDENTIAL

oxygenation at rest and during the FMD procedure. The NIRS devices are research-only devices and will not be used to make medical decisions.

Ankle-brachial index (ABI): ABI uses non-invasive oscillometric blood pressure measurements in the ankle and upper arm to provide a measure of overt or clinically occult peripheral arterial disease. It is a well-established predictor of cardiovascular events and death.⁷⁷⁻⁸⁰ We will perform automated ABI measurements using a VaSera Device (Fukuda-Denshi; Japan; 510K K115121).

Sublingual microscopy: Sublingual microcirculation will be visualized using sublingual capillaroscopy using a hand-held sublingual microscope (Microscan device; Microvision Medical; Amsterdam, Netherlands) by a trained technician.⁸¹ This is a research-only device and will not be used to make medical decisions. At least five videos of the sublingual microcirculation will be recorded from different positions and will undergo appropriate quality control.^{81,82} Videos will be analyzed using dedicated software (AVA 4.3C software; Microvision Medical; Amsterdam, Netherlands).⁸³ We will calculate the Becker score,⁸¹ which is based on the principle that density of the vessels is proportional to the number of vessels crossing arbitrary lines. In this score, three equidistant horizontal and three equidistant vertical lines are superimposed on the microscopic image and vessel density is calculated as the number of vessels crossing the lines divided by the total length of the lines. Microvascular density, our primary metric of microvascular health, will be computed as the density of vessels <20 µm in diameter. We will also compute the proportion of perfused vessels as follows: $100 \times (\text{total number of vessels} - [\text{no flow} + \text{intermittent flow}]) / \text{total number of vessels}$. Perfused vessel density, an estimate of functional capillary density, will be calculated by multiplying vessel density by the proportion of perfused vessels.^{81,84}

6-minute walk test: If they are able, participants will be asked to perform a 6-minute walk test. During this test, participants are asked to walk as far as possible during a 6-minute time interval. A corridor will be selected in which the participants can walk with minimal interference. During the procedure, one of the study staff members will supervise the test. Verbal prompts will be given, as suggested by the American Thoracic Society 2002 guidelines on the 6-minute walk procedure.⁸⁵ During the test, we will use wireless near-infrared spectroscopy (NIRS) devices to measure microvascular oxygenation as feasible. We will use two wireless portamon devices and the wireless Brite device (Artinis medical systems; The Netherlands) to measure forearm, calf and brain oxygenation at rest and during the 6-minute walk test. The NIRS devices are research-only devices and will not be used to make medical decisions.

The 6-minute walk test is an important phenotype because it offers an objective, well validated metric of exercise capacity. During this test, each patient determines the intensity of their exercise, and the test has been performed in thousands of older persons and thousands of patients with heart failure or cardiomyopathy without serious adverse events.⁸⁵ In order to be prudent, however, we will exclude patients with exertional chest pain, worsening chest pain during the previous month or a history of recent myocardial infarction (within a month), a resting heart rate of more than 120, a systolic blood pressure of more than 180 mm Hg, and a diastolic blood pressure of more than 100 mm Hg. These are consistent with current guidelines⁸⁵.

Thermal images: thermal imaging patterns depend on vascular and neural function and have been associated with cardiovascular risk factors.⁸⁶ For exploratory purposes, we will acquire thermal images of the face and bilateral hands will be obtained using a commercially available compact thermal camera (FLIR C2; FLIR, Wilsonville, OR). This device is for research only and will not be used to make medical decisions. Non-contact thermal imaging is used to detect patterns of skin surface heat emissions from patients with various conditions, which has been shown to correlate with cardiovascular disease risk. This is a non-contact procedure that is not

CONFIDENTIAL

associated with any known risks.

Breath condensate collection: Exhaled breath condensate (EBC) analysis is a developing field with tremendous promise to advance personalized, non-invasive health diagnostics as new optimized analytical instrumentation platforms and detection methods are developed.⁸⁷⁻⁹³ Exhaled breath contains potentially valuable metabolomic content due to gas exchange with blood at the pulmonary alveolar membrane interface. Various disease states often significantly change the entire pattern and relative abundances of volatile organic compounds (VOCs) in exhaled breath.⁸⁷⁻⁹³ We will collect the condensed exhaled fraction of alveolar air for about 5-8 minutes using a commercially available device (Turbo AAV 14; MEDIVAC, Parma, Italy). This system utilizes plastic air collectors coupled with a condenser equipped with a CO₂ detector that routes collection of air (via an electronic valve) only when CO₂ levels are consistent with alveolar air (as opposed to dead space air). This device is for research only and will not be used to make medical decisions. We will use only new or sterilized plastic collection tubes. Exhaled air condensate will be aliquoted and frozen at -80°C. This procedure carries no known risks.

Urine collection: In all participants, 10-mL of urine will be collected and aliquoted.

Venous endothelial cell harvesting: endothelial cells will be collected from the antecubital vein using 4 soft, flexible, sterile 0.021 inch J-wires which are briefly advanced through the standard intravenous catheter. A trained Research Nurse will place the intravenous catheter and advance the J-wire to obtain the cells. Once the J-wire is advanced and pulled back through the venous catheter, the distal portion of the wire is transferred to a 50-ml conical tube containing a buffer solution for analyses. Analyses will include RNA sequencing to assess gene expression and fixing for immunohistochemistry. This procedure will be optional depending on the availability of a trained research nurse at the time of the visit.

Venous blood collection: In all participants, we will collect 40 mL of venous blood, which will be aliquoted as plasma, serum, buffy coat (for future DNA extraction and potential future genetic testing as funding becomes available) and PAX gene tubes (for future RNA extraction).

24-hour ambulatory blood pressure monitoring: Ambulatory BP monitoring will be performed using the SunTech Oscar2 ambulatory BP monitor to obtain 24-hour brachial blood pressure measurements as well as estimates of central blood pressure⁹⁴. Prior to placement of the monitor, resting BP will be measured on both arms while sitting and orthostatic blood pressure will be checked in one arm with a standing blood pressure checked approximately 3 minutes after rising. If the difference in systolic BP is <10mmHg the non-dominant arm will be used for monitoring; however, if the difference in systolic BP is ≥10mmHg the arm with higher pressure will be used. The mid-arm circumference will be measured and recorded and a cuff appropriate for the arm circumference will be used. Participants will be instructed to engage in usual daily activities and avoid strenuous exercise for the 24-hours in which the ABPM is in place. BP will be measured every 30 minutes for 24- hours. Participants will keep a diary documenting time to bed, time waking up, medications taken, and any other events of significance.

Short Physical Performance Battery (SPPB): SPPB is a well-established and objective assessment tool to evaluate lower extremity function and mobility. It is predictive of all-cause mortality⁹⁵ and incident disability⁹⁶ and has been associated with incident cardiovascular events⁹⁷ in older adults. A study team member will administer 3 physical tests and assess the participant's balance, gait, strength, and endurance by examining their ability to stand for up to 10 seconds with feet positioned in three ways (together side-by-side, semi-tandem and tandem), time to walk 4 meters, and time to rise from a chair and return to the seated position 5 times. Each test is scored on a 0 to 4 scale using previously validated norms and summed for

CONFIDENTIAL

an overall score range of 0 to 12, with 0 indicating the lowest physical performance, and scores of 12 indicating the highest performance.⁹⁷

Other data collection:

We will perform:

- A research-grade review and quantification of available cardiac imaging studies (echocardiograms, cardiac MRIs, CT scans) in [name] imaging core lab.
- A medical record review including symptoms, past medical history, imaging, laboratory values, results of physical exams, vital signs, hemodynamic values, and other test results, with special emphasis will be placed on collection of data related to the severity of the COVID-19 episode.

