Objectives	
Primary objective: To assess organ specific phenotypes and biomarker profiles to characterize specific cardiovascular, pulmonary, renal and other abnormalities and their role in functional status, quality of life and prognosis in COVID-19 survivors.
 
Specific objectives:
 
(1) To characterize cardiac and extracardiac phenotypes in COVID-19 survivors (compared to control subjects without a history of symptomatic COVID-19), and their relationship with:
(a) quality of life; (b) functional status; (c) aerobic capacity; (d) prognosis.(2) To determine if the severity of COVID-19 is associated with measures of organ-specific structure and function after recovery.(3) To perform prospective follow-up of the cohort for the development of death, heart failure-related hospitalizations, and other adverse cardiovascular outcomes.(4) To establish a biorepository for future discovery.
Number of Subjects	200 COVID-19 survivors and 80 controls are expected to be enrolled at Penn Medicine.

CONFIDENTIAL

This material is the property of the University of Pennsylvania.

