- (1) To characterize cardiac and extracardiac phenotypes in COVID-19 survivors, and their relationship with: (a) quality of life; (b) functional status; (c) aerobic capacity; (d) prognosis.
- (2) To determine if the severity of COVID-19 is associated with measures of organ-specific structure and function after recovery.
- (3) To perform prospective follow-up of the cohort for the development of death, heart failure-related hospitalizations, and other adverse cardiovascular outcomes.
- (4) To establish a biorepository for future discovery.

3 Investigational Plan

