Participant data, blood, and urine samples will be stored for future use. These stored elements will be used only for research purposes. A randomly assigned number rather than name will identify all collected samples and data. PHI will be treated with strict confidentiality and stored in a secured, limited access area. A secure database of patient information will be maintained. PHI will not be disclosed or shared with any parties outside of the research team unless required by law or by regulatory processes at Penn (such as audits).

6 Study Monitoring, Auditing, and Inspecting

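### The plan's only blinding rule names treatment, which this cohort neither assigns nor analyses, so offline readers are not masked to COVID group or index-episode severity

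*Combined protocol and SAP*

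**What the plan says.** Section 3.1 sets the design: "This is a prospective cohort study of 200 COVID-19 survivors and 80 control subjects without a known history of symptomatic COVID-19". The comparisons of interest are stated in the objectives. Survivors' phenotypes are to be characterised "compared to control subjects without a history of symptomatic COVID-19" (synopsis, specific objective 1), and the second objective is "To determine if the severity of COVID-19 is associated with measures of organ-specific structure and function after recovery" (synopsis and Section 2). Section 4.2 powers a survivor-control difference in slopes and an association of severity with MACE.

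Blinding is mentioned once, in the aerobic-capacity paragraph of Section 3.6.1: "All data quantification will be blinded to treatment". The next sentence says of the exercise test that "we will offer this additional component to former participants of the FERMIN trial (NCT04517396").

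Elsewhere in Section 3.6.1 several measures depend on a reader, and no masking is stated for them. For carotid intima-media thickness, "A carefully trained technician will measure CIMT at these sites", helped by edge-detection software. Carotid wall tracking is semi-automated. Sublingual videos go through quality control and then software analysis. A core lab reviews and quantifies available cardiac imaging. Sections 3.1 and 3.6.2 have adjudicators identify events from hospital records, also with no masking stated. Section 5 adds that "A randomly assigned number rather than name will identify all collected samples and data".

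**The concern.** A blinding rule is useful when it hides the factor being compared. Here the factors compared are COVID group, severity of the index episode and, for the repeated measures, time. A team could follow the sentence to the letter while every reader knew who was a survivor and how ill that person had been. Nothing in the plan separates the people who recruit, examine or abstract severity from those who quantify files.

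Choosing a frame, accepting or rejecting a clip and placing or correcting an edge are points where expectation can enter. If such errors line up with the exposure, they enter the estimated difference directly, and covariate adjustment does not remove them. The comparisons at stake are survivor v control and severity v organ structure and function.

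**Working it through.** **Step 1: what the sentence can cover.** There are two readings of its factor and two of its scope.

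- *Factor: a treatment in this study.* Section 3.1 assigns none and Sections 4.1 and 4.2 analyse none, so the rule masks nothing that the study compares.
- *Factor: allocation in FERMIN.* The next sentence makes this plausible. The documents do not say so, do not describe that allocation and do not analyse it. COVID group and severity would still be unmasked.
- *Scope: exercise data only*, as its position suggests. The other modalities then have no blinding rule at all.
- *Scope: all quantification*, as its wording suggests. The rule then applies everywhere but names the wrong factor for these comparisons.

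No combination masks a reader to COVID group or severity.

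**Step 2: whether other text fills the gap.** Section 5 labels samples and data with a random number in place of a name, under record keeping and confidentiality. It does not say that readers lack access to group or severity. Nothing else in the document speaks to masking.

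**Step 3: which measures are exposed.** The text supports offline or reader-dependent quantification for carotid thickness and wall tracking, sublingual video, core-lab cardiac imaging and exercise data. Ankle-brachial index is automated, flow-mediated dilation uses a semi-automated device, and brachial pressures are oscillometric, so these are less exposed. For strain, lung B lines and muscle thickness, Table 1 does not say who reads them or when.

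**Step 4: illustration of size.** The plan has no figure to reproduce. Inputs:

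- group sizes 200 and 80 (Section 3.1);
- no true difference, and a two-sided 5% test (assumed; Section 4.2 gives 0.05 only for the severity-MACE model);
- a reading shift b in survivors of 0.1 or 0.2 SD (assumed; the documents give neither a bias nor an SD).

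Standard error in SD units: SE = √(1/200 + 1/80) = √0.0175 = 0.132.

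False-positive rate = 1 − Φ(1.96 − b/SE) + Φ(−1.96 − b/SE).

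| b (SD) | b/SE | False-positive rate |
|---|---|---|
| 0 | 0 | 5.0% |
| 0.1 | 0.76 | 11.8% |
| 0.2 | 1.51 | 32.7% |

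Measurements are taken only when feasible. If one fifth of each group lacked a measure (assumed, 160 v 64), the rates for 0.1 and 0.2 SD would be 10.4% and 27.2%.

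**Step 5: the slope analyses.** Let survivors be shifted by b at every visit. The change between visits j and k is (y_k + b) − (y_j + b) = y_k − y_j, so b drops out of the slope. Only a shift that changes from visit to visit would bias a slope difference. The table above therefore applies to a baseline mean comparison and not to the trajectory analyses.

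**The case against.** The strongest reply is that the sentence has a sensible referent. The exercise test is offered first to former FERMIN participants, who may have had an allocation, and masking exercise readers to it is reasonable. That stands, and it rules out the tempting inference that the rule guards against nothing or is simply a mistake. The supported statement is that the referent is unclear and that neither reading covers COVID group or severity.

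By position the sentence may concern exercise data alone. For carotid, sublingual and core-lab work the gap is then an omission and not a misdirected rule. That is fair, but it leaves those modalities no better protected.

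Automation is a partial answer. Edge detection and dedicated software limit judgement, so a 0.2 SD shift may be too large for some measures. A technician still measures carotid thickness, and wall tracking is only semi-automated. A reader might also infer that every ultrasound measure is read offline by a person. The text says this for carotid images but not for strain, B lines or muscle thickness.

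A reader might carry the illustration over to the 0.0025 level in Section 4.2. That level belongs to the slope comparisons, where a constant shift cancels, so it should not be combined with a baseline shift.

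Finally, full masking has practical limits. Assessments "will be repeated at approximately 18-month intervals for a total of 3 tests (except for bicycle testing, which will only occur at baseline"), so masking visit order means holding files for batch reading over about 36 months, and it is irrelevant to the bicycle test. Spirometry and tonometry depend on the operator at acquisition, which file labels cannot mask. Hospital records may reveal COVID history to adjudicators. These points stand and limit what the fix can ask for.

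**Conclusion.** The concern holds. The plan states an intention to blind quantification but names a factor outside its own comparisons, and no other text masks readers to COVID group or index-episode severity. This follows from the text and needs no assumption.

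The size is not known. Under an assumed shift of 0.1 to 0.2 SD, with 200 v 80, no true difference and a 5% test, the false-positive rate of a baseline mean comparison would be about 12% to 33%. These figures show sensitivity; they do not estimate what will happen. They do not describe the trajectory analyses, and they were not worked for the severity rank, where the mechanism is the same but the documents give no basis for a figure. Nothing in the documents shows that readers are in fact unmasked or that any measurement is biased; the finding is that the plan permits it.

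**What to change.** Replace the sentence in Section 3.6.1 with wording such as: *All offline quantification is done from files labelled only with the random study number, by readers blinded to COVID group and index-episode severity.* Place it where it governs every modality read offline, and not only the exercise test. If FERMIN allocation is also to be masked, say so in a separate sentence.

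In addition:

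- withhold phenotype results and the severity rank from event adjudicators, accepting that source records may reveal COVID history;
- mask visit order for repeated measures only where batch reading is feasible;
- list the measures that cannot be masked at acquisition, so that their comparisons are read with that in mind;
- state for each ultrasound measure whether it is read at the bedside or offline.

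The random numbers already exist, so the main cost is file labelling and some coordination so that the reader of a file does not hold the group key. Where staff are few, this may mean that someone other than the person who examined the participant reads the file. The procedure must also leave room for reporting incidental findings (Section 7.4). The change is best made before quantification starts, because files read unmasked would have to be read again.
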